6.6 Radiation adverse events

6.6.1 – Acute: Wound complications are expected in about a third of patients. Other common adverse events include: fatigue, regional alopecia, diarrhea, skin erythema, and desquamation in treatment fields.

6.6.2 – Long-term: Common long-term events include: lymphedema of the extremity receiving radiation and surgery, subcutaneous fibrosis, and joint stiffness. Less common events include bowel injury, osteoradionecrosis, and bony fracture in the radiation field. There is also a risk of secondary cancer in previously irradiated fields.

6.7 Radiation adverse event reporting

6.7.1 – This study will utilize the Common Terminology Criteria for Adverse Events (CTCAE) version 4.0 for reporting of adverse events. A copy of the CTCAE v4.0 can be downloaded from the CTEP web site.

http://ctep.cancer.gov/protocoldevelopment/electronic_applications/ctc.htm

7.0 Patient Assessments

7.1 – Study Parameters

	Pre-TX	Weekly during Proton treatment	Post Proton treatment prior to surgery	Q3 months in years 1-2 after surgery and/or postoperative proton therapy, then Q6 months in year 3-6
Pathologically confirmed dx	X			
History/Physical exam with weight	X	X	X	X
MRI and/or CT with contrast of tumor	X		X Can be either MRI or CT	Q6 months in years 1-2, then annually (either MRI or CT)
CT of chest	X			Q6 months in years 1-2, then annually
CT of abdomen & pelvis	X			
Performance status	X	X	X	X
CBC w/ diff & ANC	X			
Pregnancy test (if applicable)	X			
Thyroid function test	X If thyroid in RT field			
MSTS	X			At 12, 18, and 24 months from start of proton treatment
FACT-G	X			At 12, 18, and 24 months from start of proton treatment
Toxicity assessment		X	X	X

7.2 Pretreatment evaluation – see table above and section 3.0 for all pretreatment assessments

7.2.1 – The physician or designee will complete the Musculoskeletal Tumor Rating Scale (MSTS) prior to treatment (see Section 7.8)

7.2.2 – The patient will complete the Functional Assessment of Cancer Therapy –General (FACT-G) prior to protocol treatment

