7.6 Wound Complications and Late Radiation Morbidity

7.6.1 – Wound complications – Major wound complications, such as secondary operations, readmissions, and/or invasive procedures for wound complication (deep wound packing and/or prolonged dressing changes) will be reported

7.6.2 – Late radiation morbidity – Lymphedema, late subcutaneous fibrosis and joint stiffness arising directly from the radiation treatment, as well as limb function and physical disability, must be recorded

7.6.3 – Late subcutaneous fibrosis and joint stiffness are assessed using the European Organization for Research and Treatment of Cancer/Radiation Therapy Oncology Group (EORTC/RTOG) late toxicity scoring criteria (see Table below)

Table 1. EORTC/RTOG Late Radiation Toxicity Criteria for late subcutaneous fibrosis and joint stiffness

Tissue	Grade 0	Grade 1	Grade 2	Grade 3	Grade 4
Subcutaneous Tissue	None	Slight fibrosis; subcutaneous fat loss	Moderate fibrosis: slight field contracture	Severe fibrosis; field contracture >10%	Necrosis
Joint	None	Mild stiffness; slight range of motion loss	Moderate stiffness, pain, range of motion loss	Severe stiffness, pain, range of motion loss	Necrosis; complete fixation

7.6.4 – Lymphedema is measured according to the criteria of Stern. (see Table below)

Table 2. Stern's Rating Scale for Edema

Score	Rating
0	None
1	Mild (but definite swelling)
2	Moderate
3	Severe (considerable swelling)
4	Very severe (skin shiny and tight +/- skin cracking)

7.6.5 – The scoring criteria provided in Tables 1-2 above are specific to subcutaneous fibrosis, joint stiffness, and edema. These scales were used in a randomized phase III trial in Canada and a recent phase II RTOG trial, to which our data will be compared.^{13,16} For comparative purposes, subcutaneous fibrosis, joint stiffness, and edema should also be scored according to the CTCAE v.4.0. For grading of all other adverse events, we will use CTCAE v.4.0 only. Other late radiation morbidities, including bony fracture in the field of radiation, will be recorded.

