7.8 Musculoskeletal Tumor Rating Scale (MSTS)

7.8.1 – The MSTS³⁰ is a measure of physical function across 7 items, completed by the physician (preferably by the orthopedic surgeon or Surgical Oncologist) or the physician's designated staff. The 7 items are: pain, range of motion, strength, joint stability, joint deformity, emotional acceptance, and overall function. Each item is scored from 0-5 with a maximum possible score of 35. The MSTS has been in use for over 20 years and is a widely recognized and utilized tool used to evaluate physical function. The MSTS can be completed in approximately 10 minutes by a clinician familiar with the rating. The MSTS rating will be performed at the following time points: prior to start offing on protocol (baseline), and at 12, 18, and 24 months after start of proton radiation therapy.

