8.2 Overview and Sample size

8.2.1 – This prospective study is designed to assess late radiation toxicity. The primary endpoint is whether or not a patient experiences at least 1 of the 3 toxicities at a severity of grade 2 or greater at 2 years from start of radiation treatment. The NCIC study showed 31.5% grade 2 or greater fibrosis, 15.1% lymphedema and 17.8% joint stiffness in the preoperative arm at 2 years following treatment, and 37% of patients had at least one of these 3 toxicities at 2 years.

8.2.2 – We will test for a 20% absolute decrease in combined toxicity. A sample size of 41 patients is required to show a 20% decrease with a significance level of 0.05 and 90% power. Assuming that 5% of patients will be retrospectively ineligible and an additional 15% will not have a 2-year assessment for the primary endpoint due to death or loss to follow up, the total targeted sample size in this study is 51 patients.

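### No pre-treatment grade of edema, fibrosis or joint stiffness is scheduled, so pre-existing edema or stiffness cannot be reliably told apart from new toxicity at 2 years

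*Combined protocol and SAP*

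**What the plan says.** The schedule in section 7.1 has a row for "Toxicity assessment". It is marked weekly during protons, after protons before surgery, and in follow-up; the Pre-TX cell is empty. Section 7.2 closes the list of baseline procedures: "see table above and section 3.0 for all pretreatment assessments". Section 3.0 contains eligibility items only.

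Section 7.6.2 requires recording of "Lymphedema, late subcutaneous fibrosis and joint stiffness arising directly from the radiation treatment". Sections 7.6.3 and 7.6.4 give the scales: EORTC/RTOG for subcutaneous tissue and joint (Table 1) and Stern for edema (Table 2). Section 8.1.1 refers to 7.6.3-7.6.4 for the primary endpoint. Section 8.2.1 defines it as "whether or not a patient experiences at least 1 of the 3 toxicities at a severity of grade 2 or greater at 2 years" from the start of radiation, and cites 37% from the preoperative arm of the NCIC trial as the rate to improve on.

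Two other baseline items bear on the point. "History/Physical exam with weight" is required at Pre-TX. The MSTS is scored before treatment and at 12, 18 and 24 months; section 7.8.1 lists its content: "The 7 items are: pain, range of motion, strength, joint stability, joint deformity, emotional acceptance, and overall function".

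**The concern.** A limb sarcoma can itself cause swelling or limit a joint before any treatment. Section 7.6.2 asks the assessor to record what radiation caused, but the plan schedules no graded starting point and gives no attribution rule. Two assessors could score the same patient differently at 2 years, one counting a long-standing problem and the other discounting it, and each could claim to follow the protocol. The trial has a single arm judged against an external rate, so no concurrent control group absorbs the inconsistency.

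At stake is how the 2-year rate is interpreted. Counting pre-existing cases could hide a benefit, and discounting them could create one, depending on how the benchmark was scored. A baseline grade not taken before treatment cannot be recovered later.

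**Working it through.** **1. Is the empty cell real?** The rows for history/physical exam and performance status carry four marks, including Pre-TX. The toxicity row carries three, all in the later columns. Section 7.2 refers only to that table and section 3.0, and neither contains a Stern score or an EORTC/RTOG grade. The weekly assessments begin during treatment, and nothing designates the first of them as a baseline.

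**2. What baseline information exists for each component?**
- Edema: no score. The physical exam may mention swelling but need not grade it, and the MSTS has no edema item.
- Joint stiffness: no Table 1 grade. The MSTS scores pain, range of motion and joint deformity from 0 to 5 at baseline and 24 months, which overlaps the Table 1 joint criteria. The plan does not link it to the primary endpoint.
- Fibrosis: no Table 1 grade and no MSTS item. Little pre-existing fibrosis is to be expected, because section 3.2.5 excludes prior radiotherapy overlapping the field.

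**3. Reproducing the plan's sample size.** Inputs from 8.2: p0 = 0.37, p1 = 0.37 - 0.20 = 0.17, alpha 0.05 (taken as one-sided), power 90%.

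n = [(1.645 × √(0.37 × 0.63) + 1.282 × √(0.17 × 0.83)) / 0.20]² = 40.7, so 41, as stated.

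Total = 41 / (0.95 × 0.85) = 50.8, so 51, as stated.

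On an exact binomial test with n = 41, the largest passing count is 9 events: P(X ≤ 9) = 0.030 at 37% and 0.853 at 17%.

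**4. Can an effect be sized?** The documents give no baseline prevalence, so the inputs below are assumptions.

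(a) Pre-existing cases counted here but not in the benchmark. Let b be the share with persistent pre-existing grade 2 or greater, independent of treatment toxicity. Observed rate = 0.17 + 0.83b.

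| b | observed rate | P(X ≤ 9 of 41) |
|---|---|---|
| 0 | 17.0% | 85% |
| 2% | 18.7% | 78% |
| 5% | 21.2% | 64% |
| 10% | 25.3% | 39% |
| 15% | 29.5% | 19% |

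(b) Pre-existing cases discounted here but counted in the benchmark. With a true rate of 37% and 3, 5 or 7 points discounted, the scored rate is 34%, 32% or 30%. P(X ≤ 9) is then 6.8%, 11% or 17%, against 3.0%.

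Case (a) needs a benchmark that left pre-existing morbidity out; case (b) needs one that included it. They cannot both hold. If both trials counted it, the 37% and the 17% derived from it already contain it, and the bias at least partly cancels. The documents do not say which situation applies.

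**5. A check on b.** In 8.2.1 the benchmark had 31.5% fibrosis and 37% with any of the three. On a common denominator, 37.0 - 31.5 = 5.5% had edema or stiffness without fibrosis, among 100 - 31.5 = 68.5% without fibrosis. If the benchmark counted pre-existing edema and stiffness, and these were independent of fibrosis, their prevalence there was at most 5.5 / 68.5 = 8%. So 10% or 15% fits only a benchmark that discounted such cases, which is nowhere stated.

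**The case against.** The strongest reply is that the primary endpoint does not need a baseline. Section 8.1.1 points to the scales in 7.6.3-7.6.4, not to the attribution wording in 7.6.2, and 8.2.1 counts an absolute grade at 2 years, the same form as the benchmark. On that reading the assessor simply counts. This largely stands, and it is why the primary comparison should not change. It does not remove 7.6.2, which still asks for attribution with nothing recorded to base it on.

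A reader might infer that tumor-related and treatment-related problems cannot be separated at all. The documents do not support that: the Pre-TX exam and the baseline MSTS give partial information on stiffness. The gap is clearest for edema and weakest for fibrosis.

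A reader might also take the figures in the working as the expected loss of power or gain in false success. They are not. The prevalence and the discount are assumed, and the two cases rest on opposite assumptions about the benchmark. Nor do the documents show that tumor-related swelling persists to 2 years, after resection.

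Finally, a baseline grade would not isolate radiation: section 6.6.2 ties lymphedema to radiation and surgery together. That stands as a limit on what the change can achieve.

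**Conclusion.** The point holds as a gap in data collection. No edema, subcutaneous or joint grade on the endpoint scales is scheduled before treatment, and what is collected does not fill the gap reliably, least of all for edema. Pre-existing edema or stiffness therefore cannot be reliably told apart from new toxicity at 2 years, and attribution under 7.6.2 has no recorded basis.

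Its effect against the 37% benchmark has no derivable size or direction: the documents give neither a baseline prevalence nor the benchmark's handling of pre-existing morbidity. The point does not show that the primary endpoint is invalid or that 41 and 51 are wrong. The conclusion rests on the empty Pre-TX cell being as printed, which section 7.2 supports. The change is worth making because it is cheap and the information is lost once treatment starts.

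**What to change.** - Section 7.1: mark the toxicity row at Pre-TX. At the physical exam already scheduled, grade edema on Table 2, and subcutaneous tissue and joint on Table 1.
- Section 8: keep the absolute 2-year rate of grade 2 or greater as the primary comparison, so that it stays on the benchmark's definition.
- Section 8: report how many patients were already grade 2 or greater at baseline. Prespecify, as a supporting analysis, the rate of new or worsened grade 2 or greater toxicity at 2 years.
- Section 7.6.2: base any attribution on the recorded baseline grade.

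The cost is three extra grades per patient at an existing visit and a minor amendment. The sample size does not change. Patients already treated would have no baseline score and should be reported as such. The change supports interpretation of the primary result without altering it, and it does not separate radiation effects from surgical ones.

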7.3 Evaluation during proton radiation treatment

7.3.1 – MRI or CT with contrast of primary site should be performed 3-5 weeks after preoperative radiation therapy for surgical evaluation (surgery is done within 8 weeks after RT).

7.3.2 – Physical examination should be done weekly during radiation therapy

7.4 Evaluation after Treatment

7.4.1 – Wound complications and late radiation morbidity are reported on appropriate scales. (see section 7.6)

7.4.2 – The patient will complete FACT-G quality of life assessment at 12, 18, and 24 months from the start of radiation treatment

7.5 Failure Pattern of Recurrence

7.5.1 – All tumor recurrences including local, regional, and distant recurrence, along with second primary tumors, shall be recorded.

7.5.2 – Local tumor recurrence – Any tumor recurrence inside the CTV is defined as “in-field recurrence”; any tumor recurrence beyond the CTV to within 2 cm distance to edge of CTV is defined as “marginal recurrence” and considered “geographic miss”; any other local recurrence is defined as “outside-field recurrence”.

7.5.3 – Local tumor progression: At least a 20% increase in the maximal dimension of the primary tumor, taking as reference the smallest maximal dimension recorded since treatment started

7.5.4 – Regional tumor recurrence – Any nodal metastasis adjacent to the primary soft tissue sarcoma

7.5.5 – Distant tumor recurrence – Any tumor recurrence that develops distantly from the primary site of sarcoma

7.5.6 – Second primary tumor – Any different histology of sarcoma or any other type of malignancy inside or outside the radiation field.

7.6 Wound Complications and Late Radiation Morbidity

7.6.1 – Wound complications – Major wound complications, such as secondary operations, readmissions, and/or invasive procedures for wound complication (deep wound packing and/or prolonged dressing changes) will be reported

7.6.2 – Late radiation morbidity – Lymphedema, late subcutaneous fibrosis and joint stiffness arising directly from the radiation treatment, as well as limb function and physical disability, must be recorded

7.6.3 – Late subcutaneous fibrosis and joint stiffness are assessed using the European Organization for Research and Treatment of Cancer/Radiation Therapy Oncology Group (EORTC/RTOG) late toxicity scoring criteria (see Table below)

Table 1. EORTC/RTOG Late Radiation Toxicity Criteria for late subcutaneous fibrosis and joint stiffness

Tissue	Grade 0	Grade 1	Grade 2	Grade 3	Grade 4
Subcutaneous Tissue	None	Slight fibrosis; subcutaneous fat loss	Moderate fibrosis: slight field contracture	Severe fibrosis; field contracture >10%	Necrosis
Joint	None	Mild stiffness; slight range of motion loss	Moderate stiffness, pain, range of motion loss	Severe stiffness, pain, range of motion loss	Necrosis; complete fixation

7.6.4 – Lymphedema is measured according to the criteria of Stern. (see Table below)

Table 2. Stern's Rating Scale for Edema

Score	Rating
0	None
1	Mild (but definite swelling)
2	Moderate
3	Severe (considerable swelling)
4	Very severe (skin shiny and tight +/- skin cracking)

7.6.5 – The scoring criteria provided in Tables 1-2 above are specific to subcutaneous fibrosis, joint stiffness, and edema. These scales were used in a randomized phase III trial in Canada and a recent phase II RTOG trial, to which our data will be compared.^{13,16} For comparative purposes, subcutaneous fibrosis, joint stiffness, and edema should also be scored according to the CTCAE v.4.0. For grading of all other adverse events, we will use CTCAE v.4.0 only. Other late radiation morbidities, including bony fracture in the field of radiation, will be recorded.

7.7 Criteria for Discontinuation of Protocol Treatment

7.7.1 – Protocol treatment may be discontinued for any of the following reasons: disease progression; unacceptable adverse event; delay in protocol treatment >12 weeks.

7.7.2 – If protocol treatment is discontinued, follow up and data collection will continue as specified in protocol

7.8 Musculoskeletal Tumor Rating Scale (MSTS)

7.8.1 – The MSTS³⁰ is a measure of physical function across 7 items, completed by the physician (preferably by the orthopedic surgeon or Surgical Oncologist) or the physician's designated staff. The 7 items are: pain, range of motion, strength, joint stability, joint deformity, emotional acceptance, and overall function. Each item is scored from 0-5 with a maximum possible score of 35. The MSTS has been in use for over 20 years and is a widely recognized and utilized tool used to evaluate physical function. The MSTS can be completed in approximately 10 minutes by a clinician familiar with the rating. The MSTS rating will be performed at the following time points: prior to start offing on protocol (baseline), and at 12, 18, and 24 months after start of proton radiation therapy.

7.9 Quality of Life

7.9.1 – Patient quality of life will be assessed using the Functional Assessment of Cancer Therapy – General (FACT-G) assessment. The FACT-G³¹ is a commonly used tool measuring general quality of life across 4 scales: physical, emotional, social/family and functional well-being. It has been written at a 4th grade reading level, and a patient can generally complete the survey in 5-10 minutes. The FACT has been translated into 26 languages, and translations are accessible at the FACIT web site, <http://www.facit.org/translation/licensure.aspx>.

8.0 Statistical considerations

8.1 Study endpoints

8.1.1 – Primary endpoint – To determine the effect of reduced radiation volume with proton radiotherapy on combined late radiation toxicities (>grade 2 lymphedema, subcutaneous fibrosis, and joint stiffness) at 2 years from the start of radiation treatment using EORTC/RTOG criteria. See section 7.6.3-7.6.4.

8.1.2 – Secondary endpoints

- 8.1.2.1 – To estimate the effect of reduced radiation volume with proton radiotherapy on late radiation morbidity at 2 years from start of radiation treatment using CTCAE, v.4.0 criteria.
- 8.1.2.2 – Other CTCAE, v.4.0 grade 3-5 events
- 8.1.2.3 – To determine pattern of first failure
- 8.1.2.4 – Time to local failure
- 8.1.2.5 – Time to regional failure
- 8.1.2.6 – Time to distant failure
- 8.1.2.7 – Distant-disease free survival (distant failure or death due to any cause).
- 8.1.2.8 – Disease free survival (local, regional or distant failure or death due to any cause)
- 8.1.2.9 – Overall survival (death due to any cause)
- 8.1.2.10 – Time to second primary tumor
- 8.1.2.11 – Estimate the rate of wound complications
- 8.1.2.12 – To assess the impact of late radiation morbidity at 2 years on clinical measure, MSTS
- 8.1.2.13 – To correlate late radiation morbidity at 2 years with quality of life assessment, FACT-G
- 8.1.2.14 – Estimate the rate of tumor necrosis

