The disadvantage of preoperative radiation is the higher likelihood of postoperative wound complications.⁶⁻¹² A prospective randomized trial of preoperative versus postoperative radiotherapy by the NCIC CTG showed that the rate of wound complications increased from 17% to 35% with preoperative radiation therapy,⁶ albeit these complications were generally temporary, without significant effect on long-term function. Additionally, the NCIC trial showed that more serious chronic side effects occurred in the cohort receiving postoperative radiotherapy because those patients were generally treated to higher doses with larger treatment volumes.¹³

Combined conservative surgery and radiotherapy has been shown to achieve excellent local control in sarcoma patients following margin-negative surgery, but late radiation morbidity and reduced quality of life may result from adjuvant radiation.¹³⁻¹⁵ In the NCIC CTG trial, patients that received postoperative radiation had higher rates of grade 2 or greater fibrosis (48% versus 31.5%), increased edema (23% versus 15.1%) and joint stiffness (23% versus 17.8%).¹³ Although patients in the preoperative group had a lower rate of late effects, these effects were still substantial, occurring in 64.4% in the preoperative arm at 2 years following treatment. Increased field size and higher radiation dose were predictive of increased late effects. A prospective trial of sarcoma patients at Memorial Sloan Kettering Cancer Center, which randomized patients to postoperative adjuvant brachytherapy versus observation, showed a significant improvement in local control for patients receiving brachytherapy.⁷ The brachytherapy target region was determined by adding 2 cm margins in the superior and inferior dimensions of the tumor bed, with 1.5-2 cm

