2.0 Objectives

2.1 Primary objective

2.1.1 – To determine the effect of reduced radiation volume with proton radiotherapy on combined late radiation toxicities (>grade 2 lymphedema, subcutaneous fibrosis, and joint stiffness) at 2 years from the start of radiation treatment

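### As printed, 2.1.1 and 8.1.1 set the primary endpoint above grade 2, but 8.2.1, the benchmark and the sample size use grade 2 or greater; one definition should stand (low-severity wording correction)

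*Combined protocol and SAP*

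**What the plan says.** The threshold is stated in three places in the combined protocol and SAP.

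- **2.1.1, primary objective:** "combined late radiation toxicities (>grade 2 lymphedema, subcutaneous fibrosis, and joint stiffness) at 2 years". Section 2 appears twice in the text, with identical wording.
- **8.1.1, primary endpoint:** "combined late radiation toxicities (>grade 2 lymphedema, subcutaneous fibrosis, and joint stiffness) at 2 years from the start of radiation treatment", graded by EORTC/RTOG criteria with a pointer to 7.6.3-7.6.4.
- **8.2.1, overview and sample size:** the endpoint is whether a patient "experiences at least 1 of the 3 toxicities at a severity of grade 2 or greater at 2 years".

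The comparator is the preoperative arm of the NCIC trial. Section 8.2.1 gives 31.5% fibrosis, labelled grade 2 or greater, then 15.1% lymphedema and 17.8% joint stiffness, and adds that "37% of patients had at least one of these 3 toxicities at 2 years". The Introduction (1.1) attaches the same grade label to the 31.5%. Section 7.6.5 says that this trial's data will be compared with the Canadian randomized trial and a recent phase II RTOG trial.

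Section 8.2.2 then states: "A sample size of 41 patients is required to show a 20% decrease with a significance level of 0.05 and 90% power".

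**The concern.** Tables 1 and 2 in 7.6 run from 0 to 4 and have a separate level 2 (moderate). For joints, grade 2 is "Moderate stiffness, pain, range of motion loss". A patient whose worst toxicity is exactly grade 2 is therefore an event under 8.2.1 and not an event under the printed 8.1.1. Sections 2.1.1 and 8.1.1 also list the three toxicities as combined without a combining rule; only 8.2.1 says that any one of them suffices.

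The trial has one arm and an external benchmark, so its result depends on counting the same events on both sides. If 8.1.1 were applied as printed and the result set against 37%, moderate toxicity would count in the comparator and not here. Two printed definitions also leave a choice that could be made after the data are seen.

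**Working it through.** **1. Does the stated sample size identify the threshold?**

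Inputs from 8.2.1 and 8.2.2: benchmark p0 = 0.37; absolute decrease 0.20, so p1 = 0.17; significance level 0.05; power 90%. Sidedness and test are not stated. The single-arm normal approximation is

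n = [(z_α·√(p0(1−p0)) + z_β·√(p1(1−p1))) / (p0 − p1)]²

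With √(0.37 × 0.63) = 0.4828, √(0.17 × 0.83) = 0.3756 and z_β = 1.2816:

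- one-sided, z_α = 1.645: n = 40.7, rounded up to 41, which is the plan's figure;
- two-sided, z_α = 1.960: n = 51.0, which is not 41.

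Allowance for 5% ineligible and 15% without a 2-year assessment: 41/(0.95 × 0.85) = 50.8, or 51, again the plan's figure.

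Both figures follow from the 37% benchmark. No rate above grade 2 appears anywhere in the documents, so the endpoint as printed in 8.1.1 has no comparator and no sample-size basis in the plan.

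**2. Which wording fits the benchmark?**

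| Item | Threshold | Combining rule |
|---|---|---|
| 2.1.1 and 8.1.1 | above grade 2, as printed | none given |
| 8.2.1 endpoint | grade 2 or greater | at least 1 of 3 |
| NCIC benchmark (8.2.1) | grade 2 or greater, expressly for fibrosis | at least 1 of 3 (37%) |

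Reading the grade label as covering lymphedema, stiffness and the combined 37% is natural, but the text does not spell it out.

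**3. Direction of a mismatch.**

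Grades 3-4 are a subset of grades 2-4. In any data set the count above grade 2 cannot exceed the count at grade 2 or greater. Set against 37%, the mismatch can only make the result look better.

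**4. Size: illustration only.**

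The documents give no share of affected patients above grade 2, so the shares below are assumptions. Take 41 evaluable patients and no true benefit: 0.37 × 41 = 15.2, about 15 affected. Each patient whose worst grade is exactly 2 lowers the literal rate by 1/41 = 2.4 points.

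- 5 such patients leave 10/41 = 24.4%. The one-sided exact binomial p against 37% is 0.062. The score test gives z = (0.2439 − 0.37)/√(0.2331/41) = −1.67, p = 0.047.
- 6 leave 9/41 = 22.0%, exact p = 0.030.
- 8 leave 7/41 = 17.1%, about the whole 20-point target with no treatment effect.

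Chance of false success, P(X ≤ c) with X binomial(41, 0.37 × share):

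| Assumed share above grade 2 | Rate | c = 9 | c = 10 |
|---|---|---|---|
| matched endpoint | 0.370 | 3.0% | 6.2% |
| 90% | 0.333 | 8% | 15% |
| 80% | 0.296 | 18% | 29% |
| 60% | 0.222 | 57% | 71% |

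The plan states neither test nor cut-off. The figures move materially between the two cut-offs, so there is no firm tipping point.

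**The case against.** The strongest reply is that there may be no error in the plan at all. The age limit in 3.1.6 and the blood-count limits in 3.1.10 are also printed with a bare greater-than sign where an 'at least' sign would be usual, and an underlined sign loses its underline in plain text. Where the plan means grade 3 and above it writes a range, as in "Other CTCAE, v.4.0 grade 3-5 events". This stands as a reason to think that grade 2 or greater was intended. It does not settle the matter. A 'less than or equal' sign survives in 5.2.2, and the same greater-than sign reads naturally as strict in 7.7.1 and in Table 1. Only the source document can decide.

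Second, 8.2.1 already gives the only patient-level definition, beside the benchmark and the sample size, while 8.1.1 is worded as an objective. An analyst who follows 8.2.1 makes no error. That also stands, and it is why the point is low in severity. It does not remove the need for the section headed as the primary endpoint to state the endpoint that the design uses.

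Third, a reader might infer that the trial is biased towards success, or that the design has failed. The documents do not support either. Bias needs all three of these: the sign is real, 8.1.1 is applied instead of 8.2.1, and the result is still compared with 37%. The false-success percentages rest on assumed shares, an assumed test and an assumed cut-off, so they do not measure this trial's error rate.

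**Conclusion.** The inconsistency holds for the text as printed. Sections 2.1.1 and 8.1.1 put the threshold above grade 2 and give no combining rule; 8.2.1 puts it at grade 2 or greater in at least one of three toxicities. Only 8.2.1 is consistent with the benchmark and with 41 evaluable and 51 total. That match assumes that the grade label printed before fibrosis also covers lymphedema, stiffness and the 37%.

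If the three conditions for bias were all met, the direction would be towards success. The size cannot be estimated from the documents.

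This is a low-severity consistency correction to the primary endpoint. It takes no position on whether 37% is the right benchmark.

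**What to change.** Check the symbol in the source document. If it already reads as at least grade 2, the threshold conflict disappears, though stating the combining rule in 8.1.1 would still help.

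Otherwise, before the 2-year data are analysed, reword 2.1.1 (both copies, if the repeat is in the source) and 8.1.1 so that the endpoint is at least one of lymphedema, subcutaneous fibrosis or joint stiffness, at grade 2 or greater, 2 years after radiation starts. Keep in 8.1.1 the reference to EORTC/RTOG criteria and to 7.6.3-7.6.4, so that it stays distinct from the CTCAE endpoint in 8.1.2.1.

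The cost is one symbol check and, if needed, a wording change in two sections. The sample size stays at 41 evaluable and 51 total. No new data are needed, because Tables 1 and 2 already record every grade from 0 to 4.
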